6.1.8.2 Concomitant medications

A concomitant medication is defined as any medication that was administered during the treatment period (from Visit 1 of OLE trial). This includes medications that started before the treatment period and continued while on treatment and medications that started during the treatment period.

6.1.8.3 Age

Age will be calculated as:

$$(\text{Date of Visit 1} - \text{date of birth}) \div 365.25.$$

6.1.8.4 Exposure

The total number of dosing days in the treatment period will be calculated as:

$$(\text{Date of last IMP dose from Study Outcome eCRF form} - \text{Date of Day 1}) + 1$$

For Day 1 definition see [section 6.1.4](#)

6.1.9 Data Adjustments/Handling/Conventions

All collected data will be presented in listings. Data not subject to analysis according to this plan will not appear in any tables or graphs but will be included only in the data listings.

7. Study Patients and Demographics

7.1 Disposition of Patients and Withdrawals

Patient disposition, by site, by country and overall, will be summarized overall using standard summary statistics. Patients enrolled under Protocol / Annex will also be described. The number of patients screened, number of screen failures and number enrolled will be included.

A screen failure disposition table will be presented, including number of patients screened, number failing screening, number enrolled and the reasons for failing screening.

Patient disposition, including patients treated, patients who completed the treatment period and the taper phase, patients discontinued (including reason for discontinuation) from the treatment, and taper phases will be summarized by absolute counts (n) and percentages (%). Number and percentages of patients completing each study visit will be described. A further table split by site, and by country will be produced, showing number of patients enrolled, withdrawn at each site or in each country.

7.2 Protocol Deviations

Protocol deviations will be identified and classified.

Major protocol deviations will be summarized by type of violations for the enrolled population.

Protocol deviations will be listed. Protocol deviations due to COVID-19 will be listed separately.

7.3 Demographics and Other Baseline Characteristics

The following demographic data will be summarized overall for the safety analysis sets:

- Age (years);
- Age group (2-5 years, 6-12 years and 13-19 years);
- Sex;
- Race;
- Ethnicity
- Country;
- Region (United States, Rest of the World);

7.3.1.1 History of RTT

The following history of RTT data will be summarized by treatment group and overall for the safety analysis set:

- Type of diagnosis (Typical, Atypical).
- Main and supportive criteria for RTT diagnosis.
- Age at diagnosis (months)
- Time since last known loss of hand use or verbal language or gross motor regression (months).
- Information about the *MECP2* mutation (whether a known mutation is documented and if available, the type of mutation).
- Communication methods used by the child.
- Types of seizures that are ongoing.
- Status epilepticus.
- Whether the child lives at home or at a care home/institution.
- Most common feeding method.
- Planned method for IMP administration.

7.3.2 Medical and Surgical History and Current Medical Conditions

All conditions and diagnoses on the ‘medical and surgical history’ eCRF page will be coded using Version 21.1 of the Medical Dictionary for Regulatory Activities (MedDRA v21.1) or later version.

Only new medical history not already reported in the lead-in study will be described there.

The number of patients with relevant or significant new medical or surgical history by system organ class, and preferred term, will be summarized by absolute counts (n) and percentages (%). Percentages will be calculated based on the number of patients in the analysis population.

7.4 Exposure and Compliance

IMP is to be administered twice daily (morning and evening). The first dose will be taken on Day 1 (Visit 1). The date of final dose in the treatment period will be recorded on the eCRF under DS

form. The date of final dose, for patients who enter the taper period, will be recorded on the eCRF at the end of taper visit under DS2 form. Total number of dosing days will be reported.

8. Efficacy Analysis

The efficacy analyses will use the safety analysis set. No formal hypothesis testing will be carried out for this study. Statistical analysis will be descriptive.

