8.1.2 Dose Escalation and Dose Adjustments

The daily volumes of the GWP42003-P solution to be taken will be calculated based on the patients' weight, and the dosing schedule will be provided to the caregiver. Further information on dispensing procedures will be provided in a separate Pharmacy Manual.

Caregivers will be trained on dose administration during the GWND18064 trial.

All patients entering this OLE trial will begin dosing with 5 mg/kg/day GWP42003-P (2.5 mg/kg b.i.d.) on Day 1. Patients will be observed, and after 1 week the dose may escalate further, at the investigator's discretion, up to 15 mg/kg/day GWP42003-P (7.5 mg/kg b.i.d.) in weekly increments of 5 mg/kg/day (2.5 mg/kg b.i.d.).

Patients should then remain on a stable dose of GWP42003-P for the duration of the maintenance period of the trial (up to 104 weeks), with the option for doses to be

Study Code: GWND19002
EudraCT Number: 2019-001605-24
Clinical Protocol V2 18Dec19

decreased or increased if deemed necessary by the investigator, to a maximum dose of 20 mg/kg/day (10 mg/kg b.i.d.).

If an unacceptable AE develops at any time during the dose escalation period(s), dosing should initially be suspended or amended, at the investigator's discretion, until the event has resolved. Patients who have escalated above 5 mg/kg/day should return to the previous dose level tolerated in steps of 5 mg/kg/day each week, unless a quicker reduction is judged to be required for safety reasons. If a patient cannot tolerate 5 mg/kg/day, doses should be reduced to 2.5 mg/kg/day. If necessary, dosing may be temporarily suspended.

Patients whose dose has been decreased can have their dose increased again if tolerability improves. Patients unable to tolerate the target dose may stay at a lower dose. However, if a patient cannot tolerate a dose of 2.5 mg/kg/day, the patient should be withdrawn from treatment, unless a lower dose level is agreed in discussion with the medical monitor and can be accurately measured (minimum single-dose volume of 0.1 mL). Dose adjustments should be discussed with the GW medical monitor. The final decision regarding dose adjustments should be taken by the investigator.

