13.6.2.1 Treatment Compliance and Extent of Treatment Exposure

Treatment compliance and exposure to treatment will be summarized.

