Table 22 Scoring of Family Cohesion Item..... 45

1. Overview

This statistical analysis plan (SAP) describes the planned analysis and reporting for GW protocol number GWND19002 (An open-label extension (OLE) trial to investigate the long-term safety of cannabidiol oral solution (GWP42003-P, CBD-OS) in patients with Rett Syndrome, dated 18 December 2019 version #2.0 and corresponding protocols annex #1, version 2 dated 11 November 2020. Reference materials for this statistical plan include the protocol and the accompanying sample data collection documents. GWND19002 is the extension trial of the GWND18064 trial which will be referred to here as lead-in trial. Operational aspects related to collection and timing of planned clinical assessments are not repeated in this SAP unless relevant to the planned analysis.

The study objectives listed below are according to latest Clinical Study Protocol and Annex. Due to potential impact of the COVID-19 pandemic to patients and site personnel the Sponsor made the decision to discontinue the randomized trial (GWND18064) as well as the extension trial. Specific inclusion of patients in this extension trial is covered by the Annex. As this extension trial is stopped prematurely some planned assessments as per protocol will not be performed, see [Section 9.5](#) for complete description of the changes.

The structure and content of this SAP provides sufficient detail to meet the requirements identified by the Food and Drug Administration (FDA), European Medicines Agency (EMA), and International Conference on Harmonization (ICH) of Technical Requirements for Registration of Pharmaceuticals for Human Use: Guidance on Statistical Principles in Clinical Trials¹.

The planned analyses identified in this SAP may be included in clinical study reports (CSRs), regulatory submissions, or future manuscripts. Also, post-hoc exploratory analyses not necessarily identified in this SAP may be performed to further examine study data. Any post-hoc or unplanned, exploratory analysis performed will be clearly identified as such in the final CSR.

The statistical plan described hereafter is an *a priori* plan. It will be finalized prior to any descriptive analysis of data pertaining to study GWND19002.

2. Study Objectives and Endpoints

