3.1 Overall Design

This is a multicenter, OLE trial for patients with RTT who have completed the randomized, double blind, placebo-controlled trial (GWND18064).

Entry to this OLE trial is recommended to be on the same day as Visit 9 of the randomized controlled trial (RCT), GWND18064; however, patients may enter the OLE up to the RCT follow-up visit (Visit 11). For patients impacted by COVID-19, as per Annex, they are allowed to enroll into GWND19002 after the point of GWND18064 follow-up (Visit 11). For the ones who withdrew from GWND18064 due to COVID-19 pandemic containment measures or withdrew from GWND18064 due to sponsor administrative decision, they are allowed to enroll into GWND19002 at a later date, when appropriate.

All patients entering this OLE trial will begin dosing with 5 mg/kg/day GWP42003-P (2.5 mg/kg b.i.d.) on Day 1. Patients will be observed, and after 1 week, the dose may further be escalated, at the investigator's discretion, up to 15 mg/kg/day GWP42003-P (7.5 mg/kg b.i.d.) in weekly increments of 5 mg/kg/day (2.5 mg/kg b.i.d.). Patients should then remain on a stable dose of GWP42003-P for the duration of the maintenance period of the trial (up to 104 weeks), with the option for doses to be decreased or increased to a maximum dose of 20 mg/kg/day (10 mg/kg b.i.d.) based on clinical response and tolerability, as deemed necessary by the investigator, until the optimal dose is found. Patients whose dose has been decreased can have their dose increased again if tolerability improves. At the end of treatment (Visit 14 [Day 729]), the dose of GWP42003-P will be reduced over a 10-day taper period, and patients will enter the 4-week follow-up period.

If a patient permanently discontinues treatment at any point during the trial, GWP42003-P should be gradually reduced over 10 days (unless inadvisable due to an AE). The patient should attend a withdrawal visit (Visit 14) as soon as possible after the decision is made to permanently discontinue GWP42003-P. If applicable, the patient will taper GWP42003-P, attend the End of Taper visit (Visit 15), and then complete the 4-week follow-up period.

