6.1 Statistical Definitions and Algorithms

6.1.1 Conventions for treatment/visit naming

In all tables, listings and figures, the treatment arms will be referred to and labelled as per [Table 2](#).

Table 2 Study treatments

Endpoint	RCT Treatment	Actual Treatment	Protocol/Annex	Treatment Label (Table column/Figure legend)	Sorting order in listings, column order in tables
All	Double-Blind Treatment GWP42003-P different dosing	GWP42003-P, at different dosing	Enrolled under Protocol	Double Blind Treatment: GWP42003-P Enrolled Under Protocol	1
All	Double-Blind Treatment GWP42003-P different dosing	GWP42003-P, at different dosing	Enrolled under Annex	Double Blind Treatment: GWP42003-P Enrolled Under Annex	2
All	Double-Blind Treatment Placebo different dosing	GWP42003-P, at different dosing	Enrolled under Protocol	Double Blind Treatment: Placebo Enrolled Under Protocol	3
All	Double-Blind Treatment Placebo different dosing	GWP42003-P, at different dosing	Enrolled under Annex	Double Blind Treatment: Placebo Enrolled Under Annex	4

In all tables, listings and figures, the study visits will be referred to and labelled as per [Table 3](#).

Table 3 Study Visits

Actual Visit	Visit Label
Baseline (last record before 1 st IMP administration during lead-in trial)	RCT Baseline
Baseline (Assessment at extension Visit 1)	OLE Baseline
Visit 1: Day 1	Day 1
Visit 2: Day 8 Telephone Call	Day 8 TC
Visit 3: Day 15 Telephone Call	Day 15 TC
Visit 4: Day 29	Day 29
Visit 5: Day 57	Day 57
Visit 6: Day 85	Day 85
Visit 7: Day 141	Day 141
Visit 8: Day 197	Day 197
Visit 9: Day 281	Day 281
Visit 10: Day 365	Day 365
Visit 12: Day 547	Day 547
Visit 14: Day 729 or withdrawal	End of Treatment
Visit 15: Day 739 (end of taper)	End of Taper
Visit 16: Day 767	Follow-up

No derivation will be used for visits; data will be tabulated and listed according to the visit it was recorded under in eCRF.

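### Exposure is reported only as calendar dosing days, with no dose, patient-years or compliance summary, and no adverse event table uses person-time

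*SAP*

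**What the plan says.** **Exposure.** Protocol (V2) 13.6.2.1 states: "Treatment compliance and exposure to treatment will be summarized". SAP 7.4 is headed Exposure and Compliance, but its only output is "Total number of dosing days will be reported". SAP 6.1.8.4 gives the derivation: "The total number of dosing days in the treatment period will be calculated as" the date of last dose minus Day 1, plus 1. SAP 9.5, on departures from the protocol analysis, names only the added OLE baseline comparison.

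**Dose.** Everyone starts at 5 mg/kg/day and may go up to 20 mg/kg/day (SAP 3.1). Protocol 8.1.2 also provides for going lower, "If a patient cannot tolerate 5 mg/kg/day, doses should be reduced to 2.5 mg/kg/day", and for stopping for a time: "If necessary, dosing may be temporarily suspended". All four table columns in SAP 6.1.1 (Table 2) pool the doses as "GWP42003-P, at different dosing".

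**Adverse events.** SAP 9.1 lists patient counts and percentages by system organ class and preferred term. One table splits all TEAEs by time of first onset into seven periods. Its denominator is the safety-set patients with a visit or call in that period. SAP 7.1 reports the number completing each visit.

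**Duration of the trial.** SAP Section 1 says: "As this extension trial is stopped prematurely some planned assessments as per protocol will not be performed". SAP 9.5 says that patients who enter the extension will complete it under the protocol and annex.

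**The concern.** The primary objective is long-term safety, and to read safety data over time one needs to know how long patients were treated and with how much drug. A crude percentage of patients with an event rises with time observed, so two groups with the same underlying rate but different follow-up show different percentages. SAP 9.1 reports serious TEAEs and TEAEs leading to discontinuation only in that crude form.

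Dosing days measured as a calendar span cannot separate a patient who took drug every day from one who was off drug for weeks. They also cannot separate patients held at a low dose from those at the maximum. The protocol itself treats dose as relevant to safety: it requires hepatic monitoring at Visits 7, 11 and 13 for patients above 15 mg/kg/day (Appendix 1), and its benefit-risk section (3.3.3) relies partly on lower planned doses. Yet the liver subgroups in SAP 9.2.1 are defined by valproate, clobazam and number of antiepileptic drugs, not by dose.

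**Working it through.** The plan gives no sample size derivation or event rate to reproduce. Three checks were made.

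**1. What the onset-period table does.** The periods in SAP 9.1 were set against the visit days in SAP Table 1.

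| Period | Days | Planned visits |
|---|---|---|
| Month 1 | 1–29 | 1, 2, 3, 4 |
| Month 2 | 30–59 | 5 |
| Month 3 | 60–89 | 6 |
| Months 4–6 | 90–179 | 7 |
| Months 7–9 | 180–269 | 8 |
| Months 10–12 | 270–359 | 9 |
| Over 1 year | 360 onward | 10 to 16 |

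Every period contains a planned visit, so the fallback to the full safety set is not triggered on the planned schedule, and the denominator does shrink with dropout. Three limits remain:
- Attendance is not person-time: a patient seen once in a period counts as if observed throughout it.
- Only the first occurrence is counted, but patients who already had the event stay in the denominator.
- The last band runs from Day 360 to the final scheduled contact at Day 767, which is 767 − 360 + 1 = 408 days. The first 359 days are divided into six bands.

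**2. Crude incidence against follow-up (illustration).** The hazard λ is assumed constant; the rates are assumptions, since the documents give none. Day 729 is the planned end of treatment (104 × 7 + 1), and Day 197 is Visit 8, taken as an example of earlier stopping. Crude incidence = 1 − exp(−λ × days / 365.25).

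| Assumed first events per 100 patient-years | Day 197 | Day 729 |
|---|---|---|
| 10 | 5.3% | 18.1% |
| 25 | 12.6% | 39.3% |
| 50 | 23.6% | 63.1% |
| 100 | 41.7% | 86.4% |

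Take 50 per 100 patient-years and let a fraction of patients stop at Day 197:
- 25% stop: 0.25 × 23.64% + 0.75 × 63.14% = 53.3%.
- 75% stop: 0.75 × 23.64% + 0.25 × 63.14% = 33.5%.

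First events divided by time at risk give 50.0 per 100 patient-years in both cases.

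**3. What dosing days hide.**
- Dose: 197 days at a constant 2.5 mg/kg/day is 492.5 mg/kg, and at a constant 20 mg/kg/day it is 3,940 mg/kg, a ratio of 8. This is an outer bound, because everyone starts at 5 mg/kg/day. Staying at 5 throughout gives 985 mg/kg. Weekly steps of 5, 10 and 15, then 20 from Day 22, give 35 + 70 + 105 + 176 × 20 = 3,730 mg/kg, a ratio of 3.8. All these patients are reported as 197 dosing days.
- Interruption: an assumed 28-day suspension within 197 days leaves 169 days on drug, but 197 are reported (28/197 = 14.2%).
- Taper: SAP 7.4 takes the last treatment-period dose from the DS form and the last taper dose from DS2. SAP 6.1.8.4 names only the Study Outcome form, so it is unclear whether the 10 taper days count.

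**The case against.** **The onset-period table and the visit-completion counts already allow for follow-up.** This stands in part. A reader might infer that adverse events are reported only as crude percentages and cannot be read against follow-up at all. SAP 9.1 does not support that: the onset table has a denominator that falls with dropout. It covers all TEAEs only, however, and has the limits shown above.

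**Truncation is not established.** This stands. A reader might infer that annex patients, entering later, have shorter follow-up, so that the Table 2 columns are not comparable. No document shows that follow-up differs between those columns. Late entry does not shorten follow-up if entrants complete the schedule, as SAP 9.5 says they will; SAP Section 1 says the extension is stopped early.

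**The rates are invented and a constant hazard may be wrong.** This also stands as a limit. Protocol 3.2.2 stresses liver monitoring at the start of treatment and at dose increases, which suggests that some risks come early. If so, the contrast in crude percentages is smaller, and a rate per 100 patient-years dilutes early risk.

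**The trial is descriptive, short exposure would show in the dosing days, and dose changes are tabulated.** Dosing days and TEAEs leading to reduction, interruption or discontinuation are indeed reported. None of them gives the dose received or a rate per unit of time.

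**The missing tables may be in the shells.** SAP Section 11 places these in a separate document. The point is therefore confined to the SAP text.

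**Conclusion.** The point holds in this form: in the SAP text, exposure is a calendar span of dosing days, compliance is not summarized although the protocol says it will be, dose received and patient-years are absent, and no adverse event summary uses person-time. Serious TEAEs and TEAEs leading to discontinuation have no allowance for unequal follow-up.

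The possible size depends on the assumed rate and the follow-up pattern. Between Day 197 and Day 729, crude incidence differs by about 13 percentage points at 10 first events per 100 patient-years (18.1 − 5.3) and about 45 points at 100 (86.4 − 41.7), under a constant hazard. These figures show how the measure behaves; they do not predict a difference between the planned columns. The actual extent of truncation cannot be settled from the documents, because SAP Section 1 and SAP 9.5 conflict. This is a worthwhile and inexpensive improvement to a descriptive safety analysis, not an error that invalidates it.

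**What to change.** Keep every existing table and amend the SAP as follows.

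1. **Exposure table**, by Table 2 column and overall: total patient-years and numbers treated for at least 3, 6, 12 and 18 months. State whether taper days (DS2) count.
2. **Exposure-adjusted incidence**, by Table 2 column and overall: first events per 100 patient-years at risk for TEAEs, serious TEAEs and TEAEs leading to discontinuation. Time at risk should end at the first event and otherwise cover the same window in which events are counted.
3. **Onset table**: split the band after Day 359.
4. **Compliance**: define and summarize it, as protocol 13.6.2.1 states.
5. **Dose received**, if the database holds dosing records: mean, modal and maximum mg/kg/day, with days off drug subtracted from dosing days. This must be conditional. Caregivers confirm dosing daily and returned drug is checked (protocol 8.4 and 9.2.11), but discrepancies go to source documents. The adverse event record described in protocol 12.6 captures the action taken, with no interruption dates mentioned.
6. **Reconcile** SAP Section 1 with SAP 9.5 on whether entrants complete the extension or are stopped early.

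Items 1 to 3 need only dose and event dates that the plan already uses, so the cost is some programming. The rates assume a roughly constant hazard and should be read beside the onset-period table.

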8.1 Rett Syndrome Behaviour Questionnaire (RSBQ)

The RSBQ is a caregiver-completed questionnaire that measures the frequency of current disease characteristics (45 items) that may or may not apply to the patient. Each item is rated on a 3-point numerical scale, where all items except for item 31 (“Uses eye gaze to convey feelings, needs and wishes”) is scored as follows: 0 indicating an item that is ‘not true as far as you know’, 1 indicating an item is ‘somewhat or sometimes true’, and 2 indicating an item that is ‘very true or often true’. Item 31 is to be reverse scored, where 0 indicates that this item is ‘very true or often true’, 1 indicating that this item is ‘somewhat or sometimes true’, and 2 indicating that this item is ‘not true as far as you know’. The total maximum score is 90 and higher total scores represent greater severity.

The RSBQ score and its change from baseline (RCT Baseline and OLE Baseline) will be summarized on a numerical scale by visit.

8.1.1 RSBQ Subscales

The RSBQ includes 8 subscales: general mood, breathing problems, hand behaviors, face movements, body rocking/expressionless face, night-time behaviors, anxiety/fear, and walking/standing. The items included in each subscale are presented in [Table 4](#).

Table 4 RSBQ Subscales

Subscale	Items Included
General Mood	2, 14, 15, 16, 22, 29, 30, 36
Breathing Problems	1, 5, 6, 19, 25
Hand Behaviors	18, 20, 21, 24, 35, 43
Face Movements	4, 28, 32, 34
Body Rocking/Expressionless Face	12, 17, 31*, 33, 40, 41
Night-time Behaviors	13, 37, 42
Anxiety/Fear	7, 9, 10, 38
Walking/Standing	23, 39

* Item 31 is to be reverse scored as described in section 5.5.2.

The subscale scores are calculated by summing the scores of the items in each subscale.

Subscale scores and their change from baseline will be summarized by visit for each subscale.

